# 4 STUDY PROTOCOL

### 4.1 **OVERVIEW**

This project has the following goals:

- 1. Determine whether baseline measurements of neck strength correlate with the incidence, severity, and duration of concussion symptoms;
- 2. Determine whether a standardized neck strengthening training regime reduces the risk of concussion and the severity and duration of symptoms; and
- 3. Determine whether the relationships between neck strength and the clinical symptoms of concussion are independent of gender.

Subjects aged 5 to 22 who are involved in organized, academic or community-based contact/collision sports activities at Gustavus Adolphus College, member schools of the Independent Metro Athletic Conference (IMAC) conference, and The Sanneh Foundation participate in an instructor-led neck-strength training program. Subjects enrolled in the study will be followed for up to 3 years to assess whether the incidence, severity, and duration of concussion symptoms varies as a function of neck strength in young athletes. Anthropometric measurements, neck strength parameters, cognitive assessments, and an eye-tracking assessment will be performed for each subject at baseline, and at yearly intervals thereafter in the absence of a reported head injury. In addition, anthropometric and neck-strength measurements will be recorded at regular intervals during the study to quantify the effectiveness of the strength training regime. Subjects diagnosed with concussion during the study will be assessed for the severity and duration of postconcussion symptoms using eyetracking methodology and traditional cognitive assessments. Clinical outcomes will be assessed immediately following a concussive event and monitored by research staff until symptoms resolve. Data will be collected by onsite study volunteers trained by [name] or another member of the Brain Injury Research Lab staff at HCMC. All aspects of the study design will be overseen and approved by [name].

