# Neck Strength Parameters

HSR# 17-4360

Neck strength (extension, flexion, left and right lateral measurements) will be assessed using a hand-held commercial dynamometer that is effective for measuring neck strength. Subjects will be permitted to rest between measurements to minimize risk of injury.

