### 6.3 STATISTICAL METHODS

Data accrued through this study will be reviewed with statisticians from The Minnesota Medical Research Foundation Chronic Disease Research Group. Repeatedmeasures analysis of variance (ANOVA) will be used to evaluate the effectiveness of the training program for increased neck strength. Relationships among neck-strength parameters and concussion risk and functional outcome measures will be evaluated via logistic and linear regression models. Analyses will be adjusted for sex to evaluate whether the results are independent of gender.

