### 6.4 SAMPLE SIZE DETERMINATION

Sample size estimates were calculated based on unpublished data indicating an incidence of concussion of 11%, and published data on the reduction in concussion risk associated with increased neck strength. Based on this information, a sample of size of 1198 subjects would be needed to detect a correlation of R=0.25 between neck strength and a reduction in the severity of concussion symptoms (based on cognitive assessment scores) with a power of 0.8 at alpha=0.05. Assuming attrition of 15-20%, we therefore believe that approximately 1500 subjects will be needed.

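### Goal 3 asks whether the neck-strength/symptom relationship is the same in both sexes, but the plan only adjusts for sex, which does not compare the male and female slopes

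*Protocol*

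**What the plan says.** Section 4.1 of the protocol lists three numbered goals. The third is: "Determine whether the relationships between neck strength and the clinical symptoms of concussion are independent of gender".

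Section 6.3 names the models: "concussion risk and functional outcome measures will be evaluated via logistic and linear regression models". It then gives the approach to gender: "Analyses will be adjusted for sex to evaluate whether the results are independent of gender". The data-analysis entry of Table 1 repeats that sentence.

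No other section adds an interaction term, an analysis by sex or any other comparison of slopes. Section 6.4 sizes the study for a single overall correlation. Section 6.4.1 treats the balance of males and females only as something that affects detection of the overall neck-strength effect.

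**The concern.** The subject of Goal 3 is the relationships themselves. Its most natural reading is therefore whether the slope of symptoms on neck strength is the same in males and females.

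The protocol gives no model formula, but adjusting for sex ordinarily means adding a sex main effect. That model forces one slope on both sexes and so assumes what Goal 3 sets out to examine. It shows whether an association remains once sex is accounted for, and says nothing about whether the two slopes agree.

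The risk is a report that the relationship does not depend on gender when it exists in one sex only. The point is live here: Section 2 reports higher risk and poorer outcomes in females, and Section 6.4.1 expects fewer concussions in males. An analysis plan that followed this sentence would carry the mismatch forward, because the protocol states both the method and its purpose.

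**Working it through.** **Inputs from the protocol (Section 6.4).** 1198 subjects before attrition, 11% concussion incidence, target correlation 0.25, power 0.8, alpha 0.05.

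**Assumptions.** The protocol gives no figures by sex, so all sex-specific slopes and splits below are assumed. Severity and duration are taken as analysed in concussed subjects only. Neck strength and outcome have variance 1 within each sex, and tests are two-sided.

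**The plan's own figure.** The plan has no figure for Goal 3. For the overall correlation, Fisher's z gives n = ((1.960 + 0.842)/atanh(0.25))² + 3 = 123.3, so 124 concussed subjects, and 124/0.11 ≈ 1128. This does not reproduce 1198, but that is a separate matter and the argument does not depend on it. The stated size implies 1198 × 0.11 = 131.8, about 132 concussed subjects.

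**What the adjusted slope estimates.** With a sex main effect and no interaction, the expected slope is

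b_adj = Σ(n_s · var_s · b_s) / Σ(n_s · var_s).

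With equal variances this is the average of the two slopes weighted by the number of concussed subjects:

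- 66/66, slopes 0.25 and 0.25: (66 × 0.25 + 66 × 0.25)/132 = 0.25
- 66/66, slopes 0.50 and 0: (66 × 0.50)/132 = 0.25
- 66/66, slopes +0.25 and −0.25: 0
- 44/88, slopes 0.50 and 0: (44 × 0.50)/132 = 0.17 if the smaller group has the 0.50, or (88 × 0.50)/132 = 0.33 if the larger group has it
- 44/88, slopes +0.25 and −0.25: (44 × 0.25 − 88 × 0.25)/132 = −0.083, or +0.083 with the signs exchanged

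**How often the adjusted slope is significant** (66/66; 20,000 simulated trials per case; least squares with a sex main effect):

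| True slopes | Adjusted slope | Significant |
|---|---|---|
| 0.25 / 0.25 | 0.25 | 82.5% |
| 0.50 / 0 | 0.25 | 82.0% |
| +0.25 / −0.25 | 0 | 5.7% |

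The first two rows cannot be told apart. In a separate run of 2,000 trials per case, the interaction term was significant in 5% of trials with equal slopes, 21% with 0.35/0.15 and 85% with 0.50/0.

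**What an interaction term could deliver** (20,000 trials per case):

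| True slopes | Power, 66/66 | Power, 44/88 |
|---|---|---|
| 0.25 / 0 | 30% | 27% |
| 0.40 / 0.10 | 42% | 37–39% |
| 0.50 / 0 | 84% | 79–81% |

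The mean 95% half-width for the slope difference is 0.33–0.35 at 66/66 and 0.34–0.37 at 44/88, in SD per SD.

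By Fisher's z, 80% power for 0.25 against 0 needs 2 × ((1.960 + 0.842)/atanh(0.25))² + 3 = 243.6, so 244 per sex. That is 488 concussed subjects, or 488/0.11 ≈ 4,436 enrolled before attrition.

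**Multiplicity.** Section 4.7 measures four strength directions ("Neck strength (extension, flexion, left and right lateral measurements) will be assessed"). With severity and duration there are at least 4 × 2 = 8 interaction estimates. If they were independent tests at 0.05, the chance of at least one false positive would be 1 − 0.95⁸ = 34%. Correlated directions make it lower.

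**The case against.** The strongest reply is that a relationship independent of gender can also mean one that survives accounting for sex. Adjustment answers that question. The context gives this some support: Section 2 links sex to concussion risk and outcome, so confounding is a real issue, and Section 6.4.1 never speaks of differing slopes. On that reading goal and method agree and only the wording needs work. This stands as a possible but narrower reading. It does not remove the need to reconcile the two sections, because the goal as worded concerns the relationships and the protocol does not say that only confounding is meant.

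A second reply is that interaction terms are commonly left to the analysis plan, and adjusting for sex does not rule one out. That would hold if the protocol were silent. Instead it names adjustment as the means of evaluating independence.

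A third is that the 0.50/0 case is extreme, since one sex has twice the target correlation, and that the interaction would be badly underpowered for smaller differences. Both are true. The half-width of 0.33–0.37 exceeds the target effect of 0.25, so Goal 3 will often stay unresolved. That is a reason to report estimates with intervals and claim little. It does not make a common-slope model informative about a difference in slopes.

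**Conclusion.** The concern holds. The stated method does not serve its stated purpose under the natural reading of Goal 3. The structural point needs no assumed number: a model with one slope cannot compare two.

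The illustration (0.25 in both sexes against 0.50 in one, each giving an adjusted slope of 0.25 with about 82% significance) rests on assumed slopes, an equal split, equal strength variance and about 132 concussed subjects. Opposite slopes cancel fully only when their weighted values balance; otherwise they shrink toward zero.

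The consequence is confined to Goal 3. The primary objective and hypothesis in Sections 4.3 and 4.4 do not mention gender. This should be corrected, but it does not threaten the main analysis.

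**What to change.** Make the same edit in Section 6.3 and in the data-analysis entry of Table 1. Keep the statement that analyses are adjusted for sex, so that it still covers the ANOVA and every regression, including the one for concussion risk. Delete the clause giving the purpose of that adjustment. Then add:

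> For Goal 3, a neck-strength-by-sex interaction will be added to the regression models for concussion symptom severity and duration. The interaction estimate with its 95% confidence interval and the sex-specific slopes will be reported as supportive results. Non-significance alone will not be taken as evidence of independence.

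If only confounding by sex was intended, leave the method and reword Goal 3 to ask whether the association persists after accounting for sex.

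The edit needs no new data. Its costs are at least eight further estimates, with the multiplicity shown above, and low precision with about 132 concussed subjects. Both are reasons for the supportive label.

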#### 2 BACKGROUND

Sport-related concussion is a common injury that results in more than 200,000 emergency department visits annually, 65% of which are children aged 5 to 18. Recognized as a major public health concern, sport-related concussion diagnoses in the United States have increased by 43% overall over the last 5 years. Rates of increase over the same time span were also found to be higher for pediatric (71%) and female (up to 118%) populations, consistent with research indicating that the incidence and clinical outcomes of concussion vary with sex and age; specifically, significantly higher risks and poorer outcomes have been reported for younger and female populations. Because the developing brains of children and adolescents are uniquely vulnerable to diffuse brain injury, single or repeated concussions have potential for severe acute and long-term complications in these young athletes.

Low neck strength is a risk factor thought to contribute to an elevated concussion risk. Previous studies have shown that athletes with smaller and weaker necks experience greater resultant linear and angular head displacements, velocities, and accelerations after impact. Because these parameters represent the primary mechanisms contributing to a concussive event, further studies clarifying the relationships between neck strength and the risk and clinical outcomes of concussion are warranted. To date, only 1 study has examined the relationship between neck strength and concussion incidence; in a prospective study of high school athletes, Collins et al measured isometric neck strength parameters using a hand-held tension scale and monitored the concussion rate over several sports sessions. Neck strength was found to be a significant predictor of concussion incidence among high school students, with concussed athletes demonstrating 11% to 22% reduction in neck strength compared with nonconcussed athletes.

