Given the increases in the reported incidence of head injuries sustained by young student athletes in the United States, it is essential that high school and university athletics programs have access to inexpensive, effective, and easy-to-implement strategies for the prevention of concussions. Collectively, the results of previous studies suggest that interventions aimed at increasing athletes' neck strength may be effective for decreasing the risk and symptoms of concussion. Imperative to the development of such interventions are additional studies that quantify the extent to which the severity and duration of concussion symptoms are a function of neck strength.

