# 4.2 STUDY DESIGN AND METHODS-BRIEF

STUDY TYPE	Multicenter, observational, open analytical study
SAMPLE SIZE	1500
Sites	Sports facilities onsite at Gustavus Adolphus, member schools of the IMAC conference, and The Sanneh Foundation.
STUDY DURATION	Approximately 3 years
Study Arm(s)	Single-arm design

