#### **STUDY DESIGN** Subject recruitment and enrollment

Subjects (aged 5-22) involved in contact/collision sports programs will be recruited from and enrolled at schools and community-based sports facilities.

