#### Assessments and timeline

Demographic and sport history information will be collected at screening, and morphometric, cognitive, neck-strength, and eyetracking assessments will be made at baseline, and annually thereafter in the absence of a reported head injury. In addition, anthropometric and neck-strength measurements will be recorded immediately before and after training sessions at 6-month intervals to track improvements in neck strength. Subjects who experience concussion during the study will undergo assessments for eye-tracking and cognition at the time of the event; a subset of cognitive assessments will also be made on a daily basis following the event, until full recovery is achieved. If recovery is not achieved within a week, eye-tracking will be repeated. If symptoms continue to persist, additional cognitive assessments will be administered and repeated monthly until the subject fully recovers.

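### The neck-strength regressions name sex as their only adjustment, although the protocol itself ties concussion risk and outcome to age and enrols ages 5 to 22

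*Protocol*

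**What the plan says.** Section 6.3 and the data-analysis entry of Table 1 give the same plan: logistic and linear models relating neck-strength parameters to concussion risk and functional outcome. One covariate is named: "Analyses will be adjusted for sex to evaluate whether the results are independent of gender". No section adjusts for age, stratifies by it, or narrows the age range for these models.

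The rest of the protocol treats age as relevant:

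- Section 2 states that "the incidence and clinical outcomes of concussion vary with sex and age", and that "significantly higher risks and poorer outcomes have been reported for younger and female populations".
- Section 4.5.5 admits ages 5 to 22.
- Section 4.2 describes an observational study with a "Single-arm design", so neck strength is observed and not assigned.
- The first goal in Section 4.1 compares subjects with one another: "Determine whether baseline measurements of neck strength correlate with the incidence, severity, and duration of concussion symptoms".
- The primary hypothesis in Section 4.4 is that more neck strength goes with fewer, milder and shorter concussions.

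**The concern.** Age confounds the between-subject association if it is related both to concussion and to neck strength. The protocol supplies the first link with its direction: younger athletes do worse. The second link, that necks grow stronger between 5 and 22, is not stated but is plausible. With both, weaker-necked subjects are on average the younger ones, and a sex-only model shows a protective strength effect even if none exists. The bias points the same way as the primary hypothesis, so validity is at stake as well as precision.

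The repeated-measures ANOVA of training gains is a within-subject analysis and is not part of this point.

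**Working it through.** **Inputs from the protocol.** Section 6.4 gives N = 1198 before attrition, 11% incidence, R = 0.25, power 0.8 and alpha 0.05. Section 6.4.1 targets equal numbers of males and females. Section 4.5.5 gives ages 5–22.

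**The plan's own figure.** Two-sided Fisher z: n = ((1.960 + 0.842)/atanh 0.25)² + 3 = 123.3, so 124 concussed subjects, and 124/0.11 ≈ 1128. The stated 1198 does not reproduce exactly. Nothing below depends on that gap. Taking 1198 as given, 1198 × 0.11 = 131.8, or about 132 concussed subjects with a severity score.

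**Assumed, because the protocol gives no values.**

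- Age is scaled as (age − 13.5)/4.907, where 4.907 = 17/√12 is the standard deviation of an even 5–22 spread. Slopes per year are the same in every age mix.
- Age-strength correlation ρ over 5–22: 0.3, 0.5, 0.7 or 0.8, with strength = ρ × scaled age + √(1 − ρ²) × noise. Narrower spreads give lower realised correlations: 0.14/0.26/0.42/0.53 for ages 14–22.
- Odds ratio for concussion per 4.9 years of age: 0.7, 0.8, 0.9 or 1.0.
- True strength effect: none.

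**Concussion risk** (3000 replicates per scenario, two-sided 0.05). Percentage of trials in which the sex-adjusted model declares a strength effect:

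| Age spread | OR | ρ 0.3 | ρ 0.5 | ρ 0.7 | ρ 0.8 |
|---|---|---|---|---|---|
| Even 5–22 | 0.7 | 20 | 48 | 75 | 86 |
| 80% aged 14–22, 20% aged 5–14 | 0.7 | 15 | 34 | 61 | 75 |
| Even 10–22 | 0.7 | 8 | 18 | 33 | 46 |
| Even 14–22 | 0.7 | 5 | 8 | 11 | 16 |
| Even 5–22 | 0.8 | 11 | 21 | 40 | 48 |
| 80/20 mix | 0.8 | 8 | 16 | 27 | 39 |
| Even 10–22 | 0.8 | 6 | 9 | 17 | 22 |
| Even 14–22 | 0.8 | 5 | 6 | 8 | 10 |

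At OR 0.9 the highest rates in the four spreads are 15, 11, 8 and 6%. With age unrelated to risk they are 4–6%.

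**Severity among the 132 concussed** (10,000 replicates), age-severity correlation −0.25 over 5–22:

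| Age spread | ρ 0.3 | ρ 0.5 | ρ 0.7 | ρ 0.8 |
|---|---|---|---|---|
| Even 5–22 | 13 | 30 | 52 | 64 |
| 80/20 mix | 10 | 19 | 35 | 45 |
| Even 10–22 | 7 | 12 | 21 | 29 |
| Even 14–22 | 5 | 6 | 9 | 11 |

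A closed form confirms one cell. At ρ = 0.7 the spurious correlation has size 0.7 × 0.25 = 0.175. Then atanh(0.175) × √(132 − 3) = 2.01, and Φ(2.01 − 1.96) ≈ 0.52. At an age-severity correlation of −0.15 the highest rates in the four spreads are 27, 20, 13 and 7%.

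**With age added**, the false-significance rate is 4.1–6.0% in every scenario, and the mean strength odds ratio in the risk model is 0.99–1.01.

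**Separate check.** A 400-run simulation with normally distributed age, odds ratios of 0.75 and 0.85 per SD and ρ of 0.5 and 0.7 gave 12–59% for sex only, with spurious strength odds ratios of 0.82–0.93. Sex plus age gave 3–4%.

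**The case against.** The strongest reply is that covariate lists usually belong in the statistical analysis plan, which is not at hand. The quoted sentence also declares its purpose: it serves the gender goal and does not say that no other covariate will enter. This stands as a limit. The protocol does not show that the final analysis will omit age. But it does not leave adjustment open either: it names an adjustment twice, and leaves out the factor that its own background sets beside sex.

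The inputs can also be challenged, and much of this stands:

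- The age-strength link is not in the document, and the protocol does not say whether strength is analysed raw or scaled for body size.
- OR 0.7 per 4.9 years is steep. Over 17 years it is 0.7^(17/4.907) = 0.29, about 3.4 times the odds at age 5 as at 22. OR 0.9 gives 0.69, about 1.4 times.
- An age-severity correlation of −0.25 is as large as the effect the study is sized for. If severity were scored as change from the baseline cognitive assessment, the correlation could differ.
- The age mix is unknown. Section 2 speaks of "high school and university athletics programs", and a college is a named site. Against that, subjects "will be recruited from and enrolled at schools and community-based sports facilities", and the assent rule in Section 4.5.3 makes a separate case of children under 8.

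Finally, age is recorded, so an adjusted model can be fitted at any time. That is right. The loss is prespecification, which matters most when two defensible models disagree.

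**Conclusion.** The point holds as a cheap improvement. As written, the plan names sex alone for an observational association that age can confound in the direction of the primary hypothesis, on the protocol's own statement of how age relates to concussion.

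The size of the bias in this study is unknown. It rests on three assumptions: that neck strength rises with age, how steeply risk and severity fall with age, and how many young children enrol. If nearly all subjects are 14–22, false-significance rates stay near nominal except under the steeper assumptions. A one-fifth minority aged 5–14 raises them clearly. If risk rose with age, the bias would reverse.

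**What to change.** In Section 6.3 and in the data-analysis entry of Table 1, state: *Regression models of concussion risk, severity and duration on neck strength will adjust for age (continuous, allowing for non-linearity) and sex.* Other covariates can be left to the statistical analysis plan.

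No new data are needed. Age is an eligibility criterion in Section 4.5.5, and Table 1 says that "Demographic and sport history information will be collected at screening".

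The cost is precision. In the risk simulation, at ρ = 0.3/0.5/0.7/0.8, the standard error of the strength coefficient is multiplied by about:

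- 1.05/1.16/1.40/1.66 for ages even over 5–22
- 1.04/1.12/1.31/1.53 for the 80/20 mix
- 1.01/1.04/1.10/1.18 for ages 14–22

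These follow 1/√(1 − ρ²) using the realised correlation. Non-linear age terms were not simulated and would cost a little more.

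What this does to power depends on how R = 0.25 is read, which Section 6.4 does not say. As a partial correlation given age, the need rises only from 124 to 125 concussed subjects. As a standardised slope, power at 132 concussed falls from about 0.83 to 0.79, 0.71 and 0.55 at ρ = 0.3, 0.5 and 0.7. No new sample size follows until Section 6.4 says which is meant.

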# 4.5 STUDY ELIGIBILITY AND ENROLLMENT

#### 4.5.1 Study Population

Subjects will be youths aged 5 to 22 who are involved in one or more academic or community-based organized contact/collision athletic sports program(s). Approximately 1500 students will be recruited from Gustavus Adolphus College, member schools of the Independent Metro Athletic Conference (IMAC) conference, and The Sanneh Foundation, and enrolled in the study. The study population will be composed of players from multiple sports, and at a broad range of competitive levels. Study-site coordinators and/or trainers will be advised of the purpose and procedures of the study and will refer subjects to the Investigator for consideration. Subjects who meet all inclusion/exclusion criteria and have appropriate consent to participate in the study may be enrolled. The study is open to all races and both genders.

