# 4.5.2 Duration of Investigation

Enrolled subjects may be followed for up to 3 years. The duration of training and assessment for subjects is anticipated to vary by sport and program. However, all subjects will HSR# 17-4360

complete the neck-strengthening training program twice weekly for the duration of time that they are enrolled in the study.

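### The neck-strength regressions are stated as adjusted for sex alone, leaving sport, a possible confounder whose history is collected at screening, out of the stated model

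*Protocol*

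**What the plan says.** Section 4.2 describes the study as a "Multicenter, observational, open analytical study" with a "Single-arm design". The primary objective (4.3) is the impact of neck strength on concussion incidence and clinical outcomes.

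Section 6.3 sets the main analysis: "Relationships among neck-strength parameters and concussion risk and functional outcome measures will be evaluated via logistic and linear regression models". The next sentence reads "Analyses will be adjusted for sex to evaluate whether the results are independent of gender". The data analysis entry of the design summary in 4.2 says the same. No other covariate, stratum or offset is named in the protocol, and section 6.4.1, on complications for the analysis, discusses only an imbalance between males and females.

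Three other statements bear on sport:

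- Section 4.5.1: "The study population will be composed of players from multiple sports, and at a broad range of competitive levels".
- Section 4.5.2: "The duration of training and assessment for subjects is anticipated to vary by sport and program", with the further statement "Enrolled subjects may be followed for up to 3 years".
- Section 4.2, assessments and timeline: "Demographic and sport history information will be collected at screening".

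**The concern.** Every subject is offered the same training, so comparisons across neck strength are comparisons between athletes who differ in other ways. Nothing is randomised, and the covariates carry the inference.

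Sport is an obvious candidate for a common cause. It plausibly determines how often and how hard the head is struck, and it plausibly goes with body size and strength. Sex adjustment does not remove this, because two athletes of the same sex in different sports can differ in both respects. The varying duration by sport adds a second route: if time under observation depends on sport, so does the chance that a concussion is recorded.

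At stake is how the primary result can be read. With sport outside the model, a weak association could be a protective effect masked by sport, and a strong one could be partly a difference between sports.

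**Working it through.** **The plan's own figures.** The protocol gives no figure for this point, so there is none to reproduce. Section 6.4 supplies two inputs: 1198 subjects before attrition, and an incidence of 11%. Its attrition step reproduces, since 1198/0.80 = 1497.5, about 1500. Going the other way, 1500 × 0.80 = 1200 subjects and 1200 × 0.11 = 132 concussions. The 1198 itself is derived for a correlation of 0.25 with symptom severity. The argument here does not depend on that derivation.

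**A reference effect for incidence.** The protocol states no odds ratio, so one was constructed: the odds ratio per SD of neck strength that 1198 subjects detect with 80% power at two-sided 0.05 (the protocol does not state sidedness).

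- SE of the log odds ratio ≈ 1/√(1198 × 0.11 × 0.89) = 1/√117.28 = 0.0923
- Detectable odds ratio = exp(−2.80 × 0.0923) = 0.77

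**Assumed inputs (none is in the protocol).** Half the subjects are male. In the higher-risk sport group are 70% of males and 20% of females. Athletes in that group are 0.25 to 0.75 SD stronger within sex, and their odds of concussion are 1.5 to 3 times higher at equal strength and sex. The true odds ratio within sport is 0.77 per SD, and overall incidence is fixed at 11%.

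**Method.** Logistic data were simulated with 600,000 subjects per setting, and the model was fitted with sex alone and with sex plus sport. Power is Φ(|ln OR|/0.0923 − 1.96), keeping the SE above. The share lost is 1 − ln(OR)/ln(0.77).

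| Strength gap (SD) | Sport OR | Sex-adjusted OR | Log OR lost | Power |
|---|---|---|---|---|
| 0.25 | 1.5 | 0.788 | 9% | 0.73 |
| 0.50 | 2 | 0.819 | 24% | 0.58 |
| 0.75 | 2 | 0.838 | 32% | 0.48 |
| 0.75 | 3 | 0.890 | 55% | 0.24 |

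For the first row: |ln 0.788| = 0.238, 0.238/0.0923 = 2.58, and Φ(0.62) = 0.73. The reference of 0.77 gives about 0.80 (0.81 by the formula, because 0.77 is rounded). Repeating the simulation with another seed gave 0.78, 0.82, 0.84 and 0.89. Adding sport returned about 0.77 in every setting.

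**Direction.** With the gap reversed, so that the higher-risk group has the weaker necks, the sex-adjusted odds ratio was about 0.75 at the mild end and 0.67 to 0.68 at the extreme. Protection is then exaggerated. With no strength gap it stayed at 0.77 even with a sport odds ratio of 3.

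**A second set of assumptions.** Take two equal sport groups, no sex term and a true odds ratio of 0.75. With gaps of 0.3, 0.5 and 0.8 SD, leaving sport out gave 0.79, 0.81 and 0.85 at a sport odds ratio of 2, and 0.82, 0.85 and 0.91 at 3. Including sport gave 0.74 to 0.76.

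**Not covered.** Only incidence was simulated. Nothing was computed for the linear models of severity and duration.

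**The case against.** The strongest objection is that the sex sentence serves a particular goal, the third in section 4.1, and does not say that sex is the only covariate. A full covariate list commonly sits in the statistical analysis plan, which is not at hand, and 6.3 says the data will be reviewed with statisticians. This stands in part: the protocol does not exclude sport, and one cannot say that sport history will go unused. But the protocol does not simply defer the matter. It states an adjustment twice, for a non-randomised primary question, and an analysis that follows those words leaves sport out.

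A reader might infer that the plan hides a protective effect, because collision-sport athletes have stronger necks and more concussions. The documents do not support that. They give no strength or risk by sport, the reverse pattern would exaggerate protection, and in the settings run the attenuation never reached the null.

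It is also fair to say that the contrast between sports may be narrower than the larger assumed gaps suggest. Sections 4.1 and 4.5.1 describe contact and collision sports, although the first inclusion criterion refers more loosely to programmatic athletics. The power of 0.24 belongs to the extreme corner only; at the mild end the loss is modest.

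Finally, competitive level is not listed as a collected variable, and sport history is collected at screening, not each season. Both are correct and limit what the fix can ask for.

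**Conclusion.** The point holds in conditional form. The stated regressions adjust for sex and name nothing else, in an observational study that pools sports and expects duration to differ between them. If sport is related to both strength and risk, the sex-adjusted association is confounded, in a direction the protocol does not let one determine.

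The odds ratios of 0.79 to 0.89 against a true 0.77, and the power of 0.73 down to 0.24, rest wholly on the assumed sport mix, strength gap and sport odds ratio, and on an incidence effect size that the protocol does not itself use. They show that the bias could range from minor to serious, not that it will occur. For severity and duration the same reasoning applies in principle, without a figure.

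The change is worth making because sport history is already to be collected and the stated analysis is easily amended.

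**What to change.** In section 6.3 and in Table 1 (section 4.2), state that the logistic and linear models include sport, grouped by contact/collision level from the screening sport history, beside sex. Add competitive level if the sport history captures it; otherwise use site type (college, high school, community) as an available proxy.

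The cost is a short amendment to the analysis text and a few degrees of freedom. The risk model, with about 132 expected concussions, can carry a few grouped terms. The cost is felt most in the models restricted to those roughly 132 concussed subjects, so the grouping should be coarse and fixed before the data are examined.

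This reduces confounding by sport only. Age, which runs from 5 to 22, and time at risk, which may differ by sport and program, would remain. The simulated return to 0.77 should not be taken as a promise of an unbiased estimate, because the simulation contained no other confounder.
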